It is anticipated that the case mix in this study will be approximately 70% low risk/ 30% intermediate prognosis cases, leading to a predicted CyberKnife monotherapy 94% 5 year PSA DFS rate, with a potential range of 82% (0% favorable or low risk prognosis cases accrued) to 98% (100% favorable cases accrued). If the protocol case mix deviates from these percentages, then the protocol DFS rate required to successfully test the primary efficacy hypothesis detailed in Section 2.0 may need to be adjusted accordingly.

Table 2. Toxicity review for HDR-Monotherapy for Prostate Cancer

				>= Gd 3 toxicity	•	
HDR Details	Institution	# pts	Median f/u	Total (%)	GI (%)	GU (%)
6-7.25Gy x 6	CA Endocurie ¹⁸	117	3.3	3	0	3
9.5Gy x 4	Beaumont ¹⁹	95	4.2	8	0	8
7.5Gy x 6	Texas Tech ²⁰	145	5	5-8*	1	4 – 7*
6.5Gy x 6	Gamma West (SLC) ²¹	328	1.2	1	0	1
6Gy x 8-9	Osaka (Japan) ²²	111	2.25	7	1	6
	Totals	796	2.4	6	0 -1	5

^{*3%} acute and 4% chronic grade 3 GU toxicity – It is unclear to what degree acute and chronic grade 3 GU toxicity populations overlap in this study.

Due to short median follow-up, the incidence of >= grade 3 late toxicity is likely underestimated. We project that the incidence of late toxicity will increase by approximately 50% when all data reach 5 years maturity, yielding a projected cumulative 5 year HDR monotherapy grade 3 toxicity incidence of 9% (7-8% GU; 1-2% GI). In this study, biochemical disease-free survival (ASTRO and Phoenix definition), freedom from local recurrence, freedom from distant relapse, clinical disease-free survival, disease-specific survival and overall survival will be recorded. The incidence of grade 3 or higher toxicity and the effect of CyberKnife® radiosurgery on bladder, bowel, and sexual function will be followed and monitored using standardized, patient self-administered questionnaires and compared with results published in peer-reviewed literature for other prostate cancer therapeutic modalities. 17

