We chose N large enough to test the null hypothesis against the alternative hypothesis with power equal to 80% at the one-sided 5% significance level.

Let Z_u denote the upper u-th percentile of the standard normal distribution. Hence $Z_{.05} = 1.645$ corresponding to the one-sided 5% level of significance and $Z_{.20} = 0.84$ corresponds to 80% power. Then the sample size is determined by Formula 1:

$$N = \frac{\left[z_{\beta}\sqrt{\pi_{1}(1-\pi_{1})} + z_{\alpha}\sqrt{\pi_{0}(1-\pi_{0})}\right]^{2}}{\left[\pi_{1} - \pi_{0}\right]^{2}}, \text{ where}$$

 π_1 is the expected proportion of CyberKnife treated patients bDFS at 5 years if the alternative hypothesis is true; the bDFS rate is then expected to equal or exceed 0.94. For purposes of sample size estimation, we require 80% power if $\pi_1 \geq 0.945$. π_0 is the expected lower limit of the 95% confidence interval for π and is set equal to 0.90. Then N= 232. Allowing 8% sample size degradation for lost to follow-up, the sample size must be increased to 232/.92 = 253 subjects.

Primary Safety Objective

The primary safety objective is to establish with 95% confidence that the percentage of CyberKnife treated patients experiencing \geq Grade 3 toxicity is not more than 5% higher than the approximately 9% 5-year rate extrapolated from Table 2, Section 1.15.

With N=232 CyberKnife treated subjects, if the observed \geq Grade 3 toxicity rate equals 9%, then with 95% confidence the "true" rate \leq 12.6%. Since the difference between 12.6% and 9% is less than 5%, the sample size of 232 subjects is more than large enough to meet the primary safety objective.

11.3.1 ACCRUAL RATE: the initial three months while institutions are obtaining IRB approval, therefore we do not expect to meet the targeted monthly accrual rate until after the first three months. The estimated accrual rate is 2 patients per study site per month. Expectations of 5 treating study sites assumes an accrual period of approximately 29 months total.

11.4STATISTICAL METHODS

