11.4.1 PRIMARY OBJECTIVES

1. Efficacy

The lower limit of a one-sided 95% confidence interval for the expected proportion of patients experiencing biochemical disease-free survival (bDFS) is estimated by L, where

$$L = \frac{(2np + Z_{0.05}^2) - Z_{0.05}\sqrt{Z_{0.05}^2 + 4pn(1-p)}}{2(n + Z_{0.05}^2)}$$

Here "p" is the observed proportion of patients experiencing bDFS in either arm of the trial. The CyberKnife intervention will be considered to be effective if this study's result verifies that L is not below 90%.

2. Safety

The upper limit of a one-sided 95% confidence interval for the expected proportion of patients experiencing \geq Grade 3 gastrointestinal and genitourinary toxicity is estimated by U, where

$$U = \frac{(2np + Z_{0.05}^2) + Z_{0.05}\sqrt{Z_{0.05}^2 + 4pn(1-p)}}{2(n + Z_{0.05}^2)}$$

Here "p" is the observed proportion of patients experiencing ≥ Grade 3 gastrointestinal or genitourinary toxicity. The CyberKnife intervention will be considered to be safe if this study's result verifies that U is not more than 5% higher than the literature rate of 9%...

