- 12.5. Below are criteria for early termination of the trial (through 25%,50% and 75% enrollment of 232 patients) should an excessive number of patients experience ≥ Grade 3 gastrointestinal and genitourinary toxicity. This depends upon the number so far enrolled and a criterion that identifies too high a rate. The stopping criteria differ after 58, 116 and 174 patients have been enrolled .Consistent with Section 1.1.5, 2.0 we define an observed ≥ Grade 3 gastrointestinal and genitourinary toxicity rate of over 14% as too high. The statistical requirement is that for up to "m" patients enrolled, the number of observed cases with ≥ Grade 3 toxicity must be few enough so that there is a 95% chance that the "true" rate does not exceed 14%.

≥ Grade 3 toxicity Stopping Criteria				
Participants to	Stop study if the number of patients with grade 3-5 toxicity			
be enrolled: 253	equals or exceeds:			
	Enrollment 1-58: 4 Events			
	Enrollment 1-116: 10 Events			
	Enrollment 1-178: 17 Events			

Page 27 of 52

Regulatory Reporting: Any reports regarding safety issues and potential safety issues will also be provided to Accuray's Regulatory Affairs Department. Such reports will be evaluated and reported to the FDA and all applicable regulatory agencies, as deemed required.

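### Section 12.5 stops the trial unless low toxicity is already shown, at observed rates of 6.9% to 9.8% rather than the 14% it calls too high, and gives no stopping probabilities

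*Combined protocol and SAP*

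**What the plan says.** Section 12.5 gives criteria for ending the trial early at 25%, 50% and 75% of 232 patients, on the number with grade 3 or higher gastrointestinal and genitourinary toxicity. It defines an observed "rate of over 14% as too high". It then states the statistical requirement: the number of cases with such "toxicity must be few enough so that there is a 95% chance that the" true rate does not exceed 14%. The table says to stop when the count reaches the printed figure, starting with "Enrollment 1-58: 4 Events" and "Enrollment 1-116: 10 Events". The third figure is 17 events; the text puts that look at 174 patients and the table at 178.

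The final safety rule in Section 11.4.1 requires that "U is not more than 5% higher than the literature rate of 9" per cent, that is, a one-sided 95% upper limit of at most 14%. Section 11.3 takes as reference an "approximately 9% 5-year rate extrapolated from Table 2, Section 1.15" and concludes that "the sample size of 232 subjects is more than large enough to meet the primary safety objective". Section 1.15 describes the same figure as a "projected cumulative 5 year HDR monotherapy grade 3 toxicity incidence of 9" per cent.

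Section 12.5 gives no follow-up time for counting a patient at a look, and no probability of stopping at any true rate.

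**The concern.** A rule meant to detect too much toxicity should stop when the data indicate that the rate is too high. This one stops when the data have not yet shown that the rate is low enough. With 58 patients the two are far apart: four events, an observed 6.9%, end the study although that is below the 9% reference and half of the 14% labelled too high.

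At stake is whether a single-arm trial running as planned reaches its five-year endpoints, and how a crossing would be read. A stop would be reported as excess toxicity even though the observed rate could be below the historical comparator. The DSMB would have no stated error rates with which to interpret it.

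**Working it through.** **1. Where the boundaries come from.** Exact (Clopper-Pearson) one-sided 95% upper limits, compared with 14%:

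| Look | Last count that continues | Upper limit | First count that stops | Observed rate | Upper limit |
|---|---|---|---|---|---|
| 58 | 3 | 12.83% | 4 | 6.9% | 15.09% |
| 116 | 9 | 13.15% | 10 | 8.6% | 14.18% |
| 174 | 16 | 13.63% | 17 | 9.8% | 14.29% |

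All three printed counts reproduce at 58, 116 and 174. At 178, the table's figure, 17 events give 13.98%, so the same method would give 18. The counts belong to the text's 174.

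**2. Comparison with the final rule.** The Section 11.4.1 formula is U = [2np + z² + z√(z² + 4np(1−p))] / [2(n + z²)], with z = 1.645. At n = 232 and p = 0.09 it gives 12.58%, matching the 12.6% in Section 11.3. At n = 232 the final rule accepts up to 23 events (9.9%, U = 13.6%); 24 events give 14.1%. For 10 of 116 the same formula gives U = 13.9%. The interim table stops the trial there, although that limit satisfies the 14% criterion.

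**3. Probability of stopping, by the rate visible at the looks.** Exact binomial recursion over 58, then 58 more, then 58 more patients, stopping at 4, 10 and 17:

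| Rate visible at the looks | P(stop at any look) |
|---|---|
| 9% | 83.2% (77.8 + 4.5 + 0.9) |
| 6% | 48% |
| 4.5% | 27% |
| 3% | 10% |
| 2.25% | 4% |

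At 9% fully visible, the chance of 23 or fewer events in 232 is 73.3%. The chance of meeting that criterion without an earlier stop is 16.4%, so 1 − 16.4/73.3 = 78% of finally passing trials would have been stopped. At 14% fully visible the rule stops 99.4% of the time.

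**4. How much would be visible.** Section 11.3.1 expects 2 patients per site per month at 5 sites, or 10 per month. The first 58 patients take about 5.8 months to enrol, so their mean time on study at the first look is about 2.9 months. The documents do not give the timing of toxicity, so these are assumed profiles, each with 9% by five years, no delay from registration to treatment, and a simulation of enrolment at 10 per month:

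| Assumed timing | P(stop during enrolment) |
|---|---|
| All within 90 days | about 65% |
| Half within 90 days, rest spread to 5 years | about 15% |
| Even over 12 months | about 8% |
| One third within 90 days, rest spread to 5 years | about 5% |
| Constant hazard over 5 years | about 0% |

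Among trials that would pass the final rule, the share stopped is about 56% if all events are acute, 10% if half are, and 3% if a third are.

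**5. What this implies.** A trial at the planned 9% with half of its toxicity visible shows 4.5% at the looks. A trial at 14% with a third visible shows 14/3 = 4.7%. The rule treats the two almost alike, with about a 27% chance of stopping at 4.5%. Without a stated follow-up, the table cannot separate an on-plan trial from one that is too toxic.

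**The case against.** The strongest counter-argument concerns the 83%. A reader might infer that the trial, at its own expected rate, would stop about five times in six. The documents do not support that. The 9% is a five-year cumulative projection, and the looks are tied to numbers enrolled. Even if every event were acute, the planned accrual gives about 65%, and a delay between registration and first fraction (Section 6.2 allows up to 90 days) lowers it further. Section 1.15 expects late toxicity to grow with maturity, and the one acute/chronic split in Table 2 is 3% acute and 4% chronic. This objection stands: 83% is an upper bound.

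It can also be said that the interim and final rules share the 14% limit, that the allowed proportion rises only because n grows, and that asking for proof of safety is a legitimate conservative choice for a technique with little experience. That is fair as far as it goes, and the two rules are not flatly opposed. But Section 12.5 does not present the table as a proof-of-safety requirement; it presents it as identifying too high a rate. The shared limit does not remove the 10 of 116 mismatch either.

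Another tempting reading is that the requirement cannot be met by the first 19 patients even with no events (0.86^19 = 0.057). This has no practical effect, because the printed table governs and zero events never trigger a stop.

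Finally, Section 11.2 reports an interim analysis already done on 4,512 months over 260 subjects (about 17 months each), so the looks may be past. That limits the practical effect of an amendment but does not correct the rule as written.

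**Conclusion.** The point holds in this form. The Section 12.5 boundaries are proof-of-safety limits, described as limits for excess toxicity. They stop the trial at observed rates of 6.9%, 8.6% and 9.8%, against a stated threshold of 14% and a planned rate of 9%. That finding is exact and does not depend on event timing.

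The probability of stopping an on-plan trial does depend on timing. The range of about 0% to 65% at planned accrual rests on the assumed profiles above. If the rows were meant as the first 58, 116 and 174 patients each followed for five years, the 83% would apply, but most crossings would come after enrolment had ended. The documents do not settle which reading is meant, so the false-stop risk is unknown rather than shown to be high.

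**What to change.** Reconcile the three parts of Section 12.5 (the 14% sentence, the 95% requirement and the table, including 174 versus 178) with Sections 11.3 and 11.4.1. State how much follow-up a patient needs to be counted at a look. Re-derive the boundaries at the same looks so that they respond to evidence of excess toxicity, using the toxicity expected by the follow-up available at each look. Print beside the table the probability of stopping when toxicity is at the planned rate and when it exceeds 14%.

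The cost is a short simulation and an amendment to Section 12.5, with no extra patients. The downside is that early boundaries may become less strict than the present ones, so the DSMB should see both error rates before agreeing to them. No specific boundary is proposed here. If all three looks have already taken place, the same calculation should be documented so that any past or reported crossing can be interpreted.

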13. SOURCE OF SUBJECTS AND RECRUITMENT PROCEDURES

13.1 Source of Subjects:

13.1.1. The subjects will be male patient with low and intermediate risk organ-confined prostate cancer. The racial, gender and ethnic characteristics of the proposed subject population will reflect the demographics of the respective clinical evaluation site's surrounding area and/or patient population. Each site will attempt to recruit subjects in respective proportion to the site's respective demographics. No exclusion criteria shall be based on race or ethnicity. Subjects will be identified and recruited from outpatient facilities affiliated with sites selected to participate in this clinical study. In addition, subjects may be recruited by referrals to the clinical study sites. In the event advertisement is used for recruitment, any such advertisement will require approval by the respective site's IRB prior to use.

13.2 Recruitment Procedures:

13.1.2. After evaluation by a urologist and a radiation oncologist, patients with low and intermediate risk organ-confined prostate cancer will be offered CyberKnife treatment. After the decision is made by both the patient and his physician(s) to proceed with CyberKnife treatment, they will be screened for inclusion in the clinical evaluation. Details of the evaluation will be discussed with the patient, with ample time given for questions. If they choose to participate, the patients will be asked to sign an Informed Consent Form.

13.3 Patient Confidentiality:

13.1.3. In the attempt to maintain patient confidentiality for all patients involved in this clinical evaluation, patient identifier information will be restricted to each respective clinical site. Subject-specific identification required to conduct this evaluation (for communication purposes between the sponsor and sites) will be restricted to the number assigned to that subject at the time of registration.

14. RISK TO BENEFIT RATIO

14.1 The determination of entry into the clinical evaluation will be made independent of the decision to treat with stereotactic radiosurgery. The urologist, radiation oncologist and/or medical team performing the procedure will discuss the potential risks associated with stereotactic radiosurgery and the potential benefits of control of disease progression, despite the limited clinical experience.

14.2 Risks:

- 14.1.1. Risk classifications assigned below are based on currently available literature on treating prostate cancer with radiation therapy in a manner comparable to the radiosurgery planned for this protocol. The protocol for this clinical evaluation was designed to assure that the benefits and knowledge collected for stereotactic radiosurgery of malignant prostate tumors outweigh the potential risks to the subjects.
- 14.1.2. Risks to patients in this study include all those risks currently associated with fiducial placement as well as the risks of localizing and delivering radiation to the prostate environment. The safety of the CyberKnife system in treating intracranial tumors has been well documented. Risks of the procedure for this clinical study along with the methods to minimize the risk are described below. The radiation risks presented are categorized according to version 2.0 of the National Cancer Institute's Common Toxicity Criteria. Likely effects are listed as those side effects which occur in more than 20% of patients. Less likely effects occur in 20% or less of patients treated. Rare but serious effects occur in less than 3% of patients.
- 14.3 Risks Associated with External Radiation Therapy:
 - 14.1.3. All patients treated under this protocol will be provided with specific instructions and contact information, in the event any patient develops side effects. Many of these side effects go away shortly after radiation therapy is stopped, but in some cases side effects can be long-lasting or permanent. The following includes risks associated with external beam radiation therapy to the prostate and surrounding pelvis.

Temporary fatigue (Likely): self-limited side effect.

Temporary frequent or loose stools (likely): see notes 1 & 3. Diet changes or Imodium will be prescribed if necessary.

Temporary urinary frequency, irritation, or reduced stream (Likely): see notes 1,2,3. Alpha blocker, antispasmodic, anti-inflammatory or other appropriate symptomatic medicines will be prescribed if necessary.

Temporary redness, tanning, or hair loss of skin in the treatment area (less likely): see note 1. Topical preparations will be prescribed, if necessary.

Permanent urinary "bother", e.g. need to urinate urgently or frequently (less likely): see notes 1,2,3. Chronic alpha blocker, or other medical therapy may be required.

Permanent bowel "bother", e.g. need to move bowels urgently or frequently (less likely): see notes 1,2,3. Addition of "bulk" (e.g. Metamucil) to diet, or Imodium, may be required.

Rectal bleeding (rare, but serious): see notes 1,2,3. Hydrocortisone suppositories or enemas may be required; blood transfusions, , photocoagulation, topical chemical coagulation ,hyperbaric oxygen treatments. In extremely rare cases, colostomy may be necessary.

П

Urinary obstruction which could require catheter placement (Rare): see notes 2,3. Foley catheter, intermittent straight catheterization, or suprapubic catheter may be required.

Urethral scarring, which could impair urine stream, and could require surgery to repair (Rare, but serious): see notes 2,3. Cystoscopy, trans-urethra incision, and/or dilation may be required.

Leakage of small amounts of urine, which could require wearing pads in underwear (less likely): see notes 2,3.

Permanent inability to control urine, which could require a catheter, penile clamp, or surgery to repair (rare, but serious): see notes 2,3.

Urinary bleeding (rare, but serious): see notes 1,2,3: cystoscopy or electrocoagulation may be required. In extremely rare cases major surgery such as urinary diversion could be required.

Prostate, bladder, urethra, or rectal pain (rare): see notes 1,2,3. May require treatment with antibiotics, surgery (either open or cystoscopic), analgesics, or other medications placed in the bladder, urethra, or rectum.

Impotence (Less likely, but serious): see notes 1,2. May require treatment will medications (e.g. Viagra, Muse, etc...), other erectile aids (e.g. penile pump), or surgery (implantable penile prosthesis).

Reduction in ejaculate volume (likely), which could reduce fertility: This condition is highly likely following treatment since the target includes structures which contribute to semen.

Pain with ejaculation, or change in the sensation of orgasm (less likely): see note 2,3. May require analgesics.

Rectal or urethral ulceration, or fistula, which could result in colostomy and/or ileostomy (rare, but serious): see notes 1,2,3. Could also require antibiotics, suprapubic or Foley catheter, liquid diet, hypobaric oxygen treatments, medications or other surgeries.

Note 1: because the CyberKnife treats the prostate with over 100 beams coming from many directions, radiation dose is concentrated on the prostate. Compared with other external beam radiation devices, less radiation dose is given to the surrounding normal tissues, such as the rectum and bladder. In addition, throughout treatment, CyberKnife frequently images the prostate and corrects for movement of the patient or the prostate. This allows physicians to treat a smaller region around the prostate compared to other commonly used externally generated radiation methods. This minimizes radiation exposure to surrounding normal structures. The design characteristics of the CyberKnife thus intrinsically minimize the risk for side effects or adverse effects.

Note 2: the radiation tolerance of the normal tissues surrounding the target has been carefully considered, and likely acceptable tolerances have been calculated. These normal tissue constraints

are listed in section 8.3.2. DVH analyses will be performed as specified, to insure adherence to these constraints, thus minimizing risk.

Note 3: the large dose per fraction delivered with CyberKnife takes advantage of the low α/β ratio of prostate cancer relative to the surrounding normal structures. The hypofractionation scheme this reduces the risk of side effects or adverse effects.

14.2. Risks Associated with Fiducial Placement:

Infection (rare): In the event that a patient experiences infection as a result of fiducial placement, antiobiotic treatment will be prescribed.

14.4 Minimization of Risk:

Stringent inclusion/exclusion criteria have been incorporated into this protocol to assure that any subject who may be at increased risk from an adverse event is not enrolled into this clinical study. Subjects will be observed post procedure to assure that any acute adverse effects are detected in a timely manner so that proper medical treatment can be initiated. Subjects also will be provided with instructions as to whom to contact along with contact telephone numbers, in the event they experience any complications.

14.5 Potential Benefits:

Although previously confined to intracranial treatment, SRS is gaining recognition in the medical community as an alternative to external beam radiation therapy in other parts of the body. Use of the CyberKnife system may provide the following benefits:

- Minimally invasive procedure performed on an outpatient basis
- Lengthen interval to tumor progression
- Improved survival
- Decreased genitourinary, rectal and gastrointestinal toxicities compared with conventional radiation therapy and radical prostatectomy
- Decreased toxicities to sexual function compared to other types of radiation therapy and radical prostatectomy

14.6 Early Termination:

Subjects may withdraw or be discontinued by the investigator from the clinical evaluation at any time, however, they may be requested to continue with their follow-up PSA tests and exams five years following their last SRS treatment.

